### 11.1. Developmental Milestones

Developmental milestones will be assessed using relevant definitions obtained from the Bayley Scales of Infant and Toddler Development (version 3), and will be analyzed to assess efficacy ([Appendix 2](#) and [Appendix 3](#)). Achievement of each developmental milestone will be determined by the Physical Therapist and confirmed by the central reader (as may be necessary) based on an assessment of the submitted videos ([Section 11.3](#)). Developmental milestones will be determined at each monthly visit as listed in [Section 11.2.1](#).

During the Screening visit, the physical therapist will complete an assessment of baseline milestone achievement in accordance with [Appendix 5](#); this assessment must address all milestones/items noted on [Appendix 5](#) that are at or below the child's expected function for age, and be recorded on video. The findings must be documented in the source. Items that are below the expected function for age that are not successfully achieved during the baseline evaluation should be repeated at subsequent visits until successfully performed.

The milestones of sitting independently (items 22 and 26) should be assessed at every subsequent visit, until attainment of milestone, regardless of starting point on the scale. These milestones must also be assessed at the 18 months of age visit, regardless of previous attainment.

As the Bayley Scales do not necessarily require the child to repeat previously attained milestones, it is essential that each attained milestone be captured on video.

A milestone will be considered achieved when demonstrated by a patient and observed with video capture confirmation during a physical therapy assessment or observed with video as provided by the patient's family at the patient's visit at 18 months of age.

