### **11.3. Video Evidence**

Physical therapy assessments (Bayley Scales and CHOP-INTEND) required at each study visit will be video recorded in an effort to produce compelling, demonstrable, documented evidence of efficacy, as determined by changes in functional abilities. AveXis, Inc. (AveXis) will provide a secure and confidential upload process for transfer and storage of the videos from investigational sites to a contracted third-party vendor that will compile and arrange videos as per AveXis requirements. Any/all videos received at AveXis or the contracted vendor will be treated as confidential study data and will be the sole property of AveXis. AveXis and the contracted vendor will provide this secure, encrypted transfer and storage solution to properly protect the identities of patients/families on the videos, which may be shared with regulatory agencies, the medical community, and/or in appropriate venues to discuss the results of this clinical study.

Videos may be provided to an independent, centralized reviewer for unbiased assessment of developmental milestone achievement. The independent reviewer will document whether the video displays evidence of having achieved each developmental milestone. The date of developmental milestone achievement will be computed as the earliest date on which video evidence demonstrates the achievement of the specified milestone.

Additionally, the Parent(s)/legal guardian(s) may submit additional videos demonstrating achievement of developmental milestones at any time during the study. These videos will be handled in the same manner in which the study-derived videos are handled.

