##### 14.1.1.1. Co-Primary Efficacy Endpoint

The co-primary efficacy endpoints are:

- The proportion of patients that achieve functional independent sitting for at least 30 seconds at the 18 months of age study visit. It is defined by the Bayley Scales of Infant and Toddler Development (Version 3) ([Appendix 2](#)), confirmed by video recording, as a patient who sits up straight with the head erect for at least 30 seconds.
- The survival at 14 months of age. Survival is defined by the avoidance of the combined endpoint of either (a) death or (b) permanent ventilation, which is defined by tracheostomy or by the requirement of  $\geq 16$  hours of respiratory assistance per day (via non-invasive ventilatory support) for  $\geq 14$  consecutive days in the absence of an acute reversible illness, excluding perioperative ventilation. Permanent ventilation, so defined, is considered a surrogate for death.

An “acute reversible illness” is defined as any condition other than SMA that results in increased medical intervention (e.g., increased requirement for respiratory support; use of other concomitant medications as rescue) requirements and is expected to be reversible or improved following definitive intervention (e.g., surgery, antibiotics) or introduction of escalated supportive care, such as hospitalization (e.g., for upper respiratory infection, spontaneous fracture). The specific duration of the condition antecedent intervention shall not be considered in the definition of “acute.” The date of “definitive intervention” shall be defined as the date of provision of a procedure (e.g., surgery, etc.) or medication (e.g., antibiotics) intended to cure or substantially improve the condition. For conditions such as viral respiratory infections for which supportive care is provided, the date of “definitive intervention” shall be considered the date of hospitalization or substantial escalation of care.

█ [REDACTED]  
█ [REDACTED]  
█ [REDACTED]  
█ [REDACTED]  
█ [REDACTED]  
█ [REDACTED]  
█ [REDACTED]

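### The milestone-achievement rule in Section 11.1 does not match the visit-based definition of the first co-primary endpoint, and the protocol does not say which one decides who is a sitter

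*Protocol*

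**What the plan says.** **Endpoint.** Protocol Section 14.1.1.1 defines the first co-primary endpoint as "The proportion of patients that achieve functional independent sitting for at least 30 seconds at the 18 months of age study visit", and describes a responder as "confirmed by video recording, as a patient who sits up straight with the head erect for at least 30 seconds". It does not say who makes or reads the recording.

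**Achievement rule.** Section 11.1 states: "A milestone will be considered achieved when demonstrated by a patient and observed with video capture confirmation during a physical therapy assessment". No visit is named. The sentence then adds a second route, namely "observed with video as provided by the patient's family at the patient's visit at 18 months of age". The rule covers milestones in general and does not set sitting apart.

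**Re-test.** Section 11.1 also requires the two sitting items, 22 and 26, to be assessed at the 18-month visit whether or not the child has already passed them.

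**Family videos.** Under Section 11.3, parents or guardians "may submit additional videos demonstrating achievement of developmental milestones at any time during the study", and "These videos will be handled in the same manner in which the study-derived videos are handled". The same section sets the date rule: "The date of developmental milestone achievement will be computed as the earliest date on which video evidence demonstrates the achievement of the specified milestone".

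**Independent reading.** Section 11.3 says: "Videos may be provided to an independent, centralized reviewer for unbiased assessment of developmental milestone achievement". Sections 11.1 and 11.2.1 and footnote e of Appendix 5 are equally permissive. Section 9.4 confirms that the study is open-label.

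**Test.** Sections 14.2 and 14.3.2 compare the sitting proportion with 0.1% by a one-sided exact binomial test at 0.025. Survival is tested only if that test rejects. Section 14.3.1 says that observed data are used when data are missing.

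**The concern.** The protocol carries two rules that can classify the same child differently on its first co-primary endpoint. One asks what the child does at the 18-month visit. The other asks whether the child has ever been filmed doing it with a therapist, or appears doing it on a video supplied by the family. A home clip is not a standardised assessment: the number of attempts and any support out of frame are unknown, and a skill filmed earlier may have been lost by 18 months.

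Two things are at stake. The rejection threshold may be so low that a single classification matters. And the sitting proportion, which will be the headline estimate whatever the test shows, depends on which rule the analyst applies.

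**Working it through.** **1. The two rules side by side**

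| Child | Section 14.1.1.1 | Section 11.1 achievement rule |
|---|---|---|
| Sits on video with the therapist at the 18-month visit | Sitter | Achieved |
| Sat on video with the therapist at an earlier monthly visit, but not at 18 months | Not a sitter | Achieved |
| Does not sit at the 18-month visit; family hands over a clip filmed earlier | Not a sitter | Achieved if the phrase describes hand-over; not achieved by this clause if it describes when the child sat |
| Does not sit for the therapist at 18 months; family clip filmed at that visit | Unclear: video is required, but no assessor or recorder is named | Achieved on either reading |

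The rules agree in the first row. In the second they differ, although the mandatory re-test suggests that the visit result was meant to govern. In the third and fourth rows the family clause may credit a child who did not perform the item with the therapist, and nothing in the protocol resolves this.

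**2. The plan's own power figure**

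Inputs from Section 14.2: null rate 0.1%, one-sided alpha 0.025, 15 patients meeting ITT criteria, about 30% excluded (15 × 0.7 = 10.5, so 10 or 11 analysed), true rate 30% to 40%, stated power above 90%.

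With a threshold of one sitter, the attained size is P(X ≥ 1) = 1 − 0.999^n:
- n = 10: 0.0100
- n = 11: 0.0109
- n = 15: 0.0149

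All are below 0.025, so one sitter is enough to reject. Power is 1 − (1 − p)^n:
- n = 10: 0.972 at 30%, 0.994 at 40%
- n = 11: 0.980 and 0.996
- n = 15: 0.995 and 0.9995

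The stated power is reproduced. The threshold stays at one sitter up to n = 25 (0.0247) and is lost at n = 26 (0.0257).

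**3. What one child is worth**

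In the estimate, one child is 1/15 = 6.7 percentage points, or 1/10 = 10 points. In the test, one child is the difference between no rejection and rejection if no other child sits. At the planned true rates, the chance that no child truly sits is 1 minus the power above: 0.5% (30%) or 0.05% (40%) at n = 15, and 2.8% or 0.6% at n = 10.

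**4. Illustration under a null drug effect**

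The documents give no rate of wrongly credited sitting, so f below is assumed. With f added to the 0.1% null, P(at least one credited) = 1 − [0.999 × (1 − f)]^n:

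| Assumed f per child | n = 10 | n = 15 |
|---|---|---|
| 0.5% | 5.8% | 8.6% |
| 1% | 10.5% | 15.3% |
| 2% | 19.1% | 27.2% |
| 5% | 40.7% | 54.4% |

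This shows sensitivity to f. It does not estimate f.

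**The case against.** The strongest reply is that the endpoint definition is clear and specific. The 18-month visit is named in the objectives, the endpoint section and the hypotheses, whereas the achievement sentence in Section 11.1 is a general rule for a list of milestones and never mentions primary responder status. A specific definition normally prevails over a general one. The compulsory re-test of items 22 and 26 fits an endpoint on which earlier success does not count. This largely answers the earlier-visit route, which is the weaker part of the point. It does not dispose of it, because the re-test sentence does not say that its result alone decides, and the achievement rule follows without qualification.

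On family videos, the wording can mean filmed at 18 months or handed over at 18 months. The instruction to handle them like study videos may concern only transfer, storage and review, and the earliest-date rule concerns dating. All of this is fair. Even so, on either reading of Section 11.1 a recording made outside a therapist's assessment can establish a milestone, with no carve-out for the primary one.

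A reader might infer that the open-label sites choose which recordings are independently read. The protocol does not say that. Reading is optional and the chooser is not named; Section 11.3 sends videos to a third-party vendor working to the sponsor's requirements.

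The analysis plan, not shown here, may define the derivation. That would not remove the mismatch between two sections of the protocol.

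**Conclusion.** The point holds as an unreconciled conflict between Section 14.1.1.1 and the achievement rule in Section 11.1. It is stronger for family videos and weaker for earlier visits, and it should be corrected. Its weight comes from the single-sitter threshold (P = 0.0149 at n = 15, 0.0100 at n = 10), from the gate to the survival test, and from the 6.7 to 10 points that each child contributes to the reported proportion.

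Two stronger conclusions do not follow. First, a reader might infer that a child who sat only at an earlier visit is a primary success under the protocol. The endpoint definition does not count that child; the fault is that Section 11.1 does not say so. Second, a reader might infer from the illustration that the trial's false-positive rate is some tens of per cent. Those figures rest wholly on assumed rates and apply only if no child truly sits. At the planned 30% to 40%, that has a probability of at most 2.8%, and Section 5.4 reports 8 of 12 Phase 1 Cohort 2 patients sitting unassisted. A wrongly credited sitter would also only open the survival test, which must still succeed by itself. The more likely practical effect is therefore on the estimate.

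**What to change.** 1. State in Sections 11.1 and 14.1.1.1 that primary responder status rests only on Bayley gross motor item 26, performed with the physical therapist and video-recorded at the 18-month visit, within its 0 to 14 day window.
2. State that family videos and earlier attainment are used only for milestone dates and supportive summaries.
3. State how a patient with no 18-month assessment is classified, and reconcile this with the observed-data rule in Section 14.3.1.
4. Where the existing central-reader route is available, send every ITT patient's 18-month item 26 recording through it, in place of the optional wording. This is separable from items 1 to 3. Making the central reading itself the endpoint would be a larger and more debatable change, because the protocol describes a contracted video vendor but does not confirm a contracted reader.

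The cost of items 1 to 3 is amendment wording, since item 26 is already mandatory and already filmed at that visit. Item 4 adds the reading of about 15 recordings. The drawback is that a child who can sit but does not perform within the window is not counted as a sitter.

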## 11.2. Motor Function Tests

### 11.2.1. Bayley Scales of Infant and Toddler Development/Developmental Milestones

The Bayley Scales of Infant and Toddler Development (Version 3) ([Appendix 2](#)) is a standardized, norm-referenced infant assessment of developmental functioning across 5 domains of cognitive, language, motor, social-emotional, and adaptive behavior. The Bayley Scales will be administered by a qualified Physical Therapist.

The full Bayley Scales will be administered at screening, every 6 months starting at Month 6, and at End of Study when the patient reaches 18 months of age (or early termination), whereas the gross and fine motor subtests of the motor domain will be administered at each monthly visit. For patients in which English is not their first language, the language subtests (receptive communication and expressive communication) and cognitive scale portions of the Bayley will not be performed.

Each Bayley Scales/developmental milestone assessment will be video recorded in accordance with the AVXS-101-CL-303 Video Manual and may be submitted to the vendor for review by a central reader ([Section 11.3](#)).

The following developmental milestones will be assessed:

- Ability to hold head erect without support
- Ability to roll from back to both sides
- Ability to sit with support
- Ability to sit independently, > 10 seconds; WHO [22]
- Ability to sit without support for at least 30 seconds
- Ability to crawl
- Ability to pull to stand
- Ability to stand with assistance
- Ability to stand alone
- Ability to walk with assistance
- Ability to walk alone

### 11.2.2. CHOP-INTEND

The CHOP-INTEND is a motor function scale developed and validated for use specifically to monitor motor function status and decline amongst children with SMA Type 1, and will be administered by a qualified Physical Therapist.[23,24] The CHOP-INTEND scale examines several aspects of motor function, including head control, righting reactions, and trunk movements in supported sitting, supine, and prone positions ([Appendix 4](#)). Anti-gravity movements in assisted rolling, ventral suspension, and supported standing will also be measured.

The CHOP-INTEND will be performed at screening, Day -1, and at each scheduled visit from Day 7 through the End of Study when the patient reaches 18 months of age (or early termination) ([Appendix 5](#)). If Day -1 CHOP-INTEND assessment cannot be conducted, a CHOP-INTEND assessment must be completed on Day 1 prior to dose administration.

Patients who achieve 3 consecutive CHOP-INTEND scores  $\geq 58$  will not undergo any additional CHOP-INTEND examinations.

Each CHOP-INTEND exam will be video recorded in accordance with the AVXS-101-CL-303 Video Manual and submitted to the vendor for review by a central reader as may be necessary ([Section 11.3](#)).

### **11.3. Video Evidence**

Physical therapy assessments (Bayley Scales and CHOP-INTEND) required at each study visit will be video recorded in an effort to produce compelling, demonstrable, documented evidence of efficacy, as determined by changes in functional abilities. AveXis, Inc. (AveXis) will provide a secure and confidential upload process for transfer and storage of the videos from investigational sites to a contracted third-party vendor that will compile and arrange videos as per AveXis requirements. Any/all videos received at AveXis or the contracted vendor will be treated as confidential study data and will be the sole property of AveXis. AveXis and the contracted vendor will provide this secure, encrypted transfer and storage solution to properly protect the identities of patients/families on the videos, which may be shared with regulatory agencies, the medical community, and/or in appropriate venues to discuss the results of this clinical study.

Videos may be provided to an independent, centralized reviewer for unbiased assessment of developmental milestone achievement. The independent reviewer will document whether the video displays evidence of having achieved each developmental milestone. The date of developmental milestone achievement will be computed as the earliest date on which video evidence demonstrates the achievement of the specified milestone.

Additionally, the Parent(s)/legal guardian(s) may submit additional videos demonstrating achievement of developmental milestones at any time during the study. These videos will be handled in the same manner in which the study-derived videos are handled.

### **11.4. Compound Motor Action Potential**

Peroneal nerve CMAP amplitude will be measured by a qualified electrophysiologist, at all clinical sites capable of performing this assessment, using the procedures as described in the CMAP Manual ([Appendix 5](#)). CMAP will be measured at screening, every 6 months starting at Month 6, and End of Study when the patient reaches 18 months of age (or early termination) ([Appendix 5](#)).

The CMAP data will be collected for centralized review and interpretation.

Sites that do not have equipment or appropriately experienced personnel required to perform CMAP measurements will not be required to perform these assessments.

## 12. ASSESSMENT OF SAFETY

### 12.1. Safety Parameters

Safety parameters include physical examinations, pulmonary examinations, vital signs, capillary blood gas assessments, weight and length measurements, 12-lead electrocardiograms (ECGs), 12-lead Holter monitor recordings, echocardiograms, swallowing tests, laboratory assessments, adverse event monitoring, and photographs of the infusion site. In general, safety assessments will be performed at the times specified in the Table of Assessments ([Appendix 5](#)). All post-treatment visits are relative to the date on which gene replacement therapy is administered until the patient reaches 14 months of age, at which point all visits are relative to the patient's date of birth.

Unless otherwise noted, visit windows for the outpatient follow-up visits are as follows:

- Days 7, 14, 21, and 30:  $\pm 2$  days
- Monthly visits starting at Month 2:  $\pm 7$  days
- 14 months of age visit: 0 to 14 days **after** the patient reaches 14 months of age
- 18 months of age/End of Study visit: 0 to 14 days **after** the patient reaches 18 months of age

#### 12.1.1. Demographic/Medical History

Demographic/medical history information will be collected at screening and captured in the eCRF. Information that will be collected includes:

- Familial history of SMA including affected siblings or parent carriers
- Gestational age at birth
- Length/weight/head circumference at birth
- Hospitalization information from time of birth including number, duration, and reason for hospitalizations including International Statistical Classification of Diseases and Related Health Problems (ICD-10 codes), if available
- Historical ventilatory support, if any
- Historical feeding support, if any

Patients are encouraged to follow all routinely scheduled immunizations, as recommended by the Center for Disease Control (CDC), throughout the study. Seasonal vaccinations that include palivizumab prophylaxis (also known as Synagis) to prevent respiratory syncytial virus (RSV) infections are also recommended in accordance with American Academy of Pediatrics [[26](#)].

#### 12.1.2. Physical Examinations

Physical examinations will be conducted by the Investigator or Sub-Investigator at each scheduled visit, except Day -1 ([Appendix 5](#)). The Day 1 physical examination will be

performed prior to the start of gene replacement therapy infusion. Physical examinations include a review of the following systems: head, eyes, ears, nose and throat (HEENT), lungs/thorax, cardiovascular, abdomen, musculoskeletal, neurologic, dermatologic, lymphatic, and genitourinary.

### **12.1.3. Vital Signs/Weight and Length**

Vital sign parameters include blood pressure, respiratory rate, pulse, axillary temperature, and pulse oximetry. Vital signs will be obtained at each study visit (as specified in [Appendix 5](#)). On Day 1, vital signs will be continuously monitored throughout the gene replacement therapy infusion and recorded pre-dose and every 15 ( $\pm$  5) minutes for the first 4 hours after the start of infusion, and then every hour ( $\pm$  15 minutes) until 24 hours after the start of infusion. Axillary temperature will be recorded pre- and post-infusion.

Weight and length will be measured at each study visit (as specified in [Appendix 5](#)). On Day 1, weight and length will be measured pre-dose.

### **12.1.4. Electrocardiogram**

A 12-lead ECG will be performed at screening, Day -1, pre-dose on Day 1, Day 2, Months 3, 6, 9, and 12 visits and every 6 months thereafter. A 12-lead ECG will also be performed at the End of Study visit when the patient reaches 18 months of age (or early termination) ([Appendix 5](#)). For patients enrolled in the study prior to amendment 3 and irrespective of the study schedule, after signing an updated informed consent form, a 12-lead ECG will be conducted at the next scheduled visit and then in accordance with the Schedule of Assessments ([Appendix 5](#)). Additional ECG monitoring will be at the discretion of the Investigator as per local institutional guidelines.

The ECG will be interpreted locally by a cardiologist. The ECG tracings or ECG machine data will be collected for centralized review and interpretation by a cardiologist.

